Preliminary analyses will include descriptive statistics to examine the distributional and psychometric properties of the variables (e.g., normality, internal consistency). Variables will be transformed to achieve normality if necessary. We will also examine post-inclusion attrition by comparing study completers to dropouts on sociodemographic, baseline, and length of admission data to determine if they differ systematically. Preliminary analyses may also include analyses of adverse events, progress of recruitment and retention, and quality markers as the study progresses. In keeping with the intention to treat principle, missing data will be handled with multiple imputations (m=20) with assumptions checked with sensitivity analyses [43,44] [32]. Our main analysis will not adjust for covariates other than baseline value of the outcome and design factors (balancing factors used in the urn randomization procedure) under the assumption that randomization produced groups balanced on measured and unmeasured confounders. Additionally, the data from this study across all Aims will be combined with data from subjects who completed neuroimaging procedures in PVAMC IRB protocol #2018-051.

Data from this study, across all Aims, will also be combined with data from subjects who completed procedures for PVAMC IRB protocol #IRB-2020-008. Data from this study related to recorded interviews, de-identified with the exception of assessment dates, will also be shared with the PVAMC research study “Longitudinal Assessment of the Sleep-Suicide Link in Veterans Discharged from Inpatient Psychiatric Care” (IRB-2020-008), for training of staff and inter-rater reliability analysis (i.e., to calculate agreement across interviewers and to make final decisions on ratings).

E2. Aim 1 Analytical Plan (Analyses Related to Treatment)

The data from this study for Aim 1 may be combined with data from subjects who completed neuroimaging procedures in PVAMC IRB protocol #2018-051. Data from this study, for Aim 1 may also be combined with data from subjects who completed procedures for PVAMC IRB protocol #IRB-2020-008.

E2.1 Interim analysis and early stopping of treatment

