We will conduct 1 interim analysis and assess our primary aim when we have enrolled 32 persons per treatment group (~50% enrollment). The analyst and investigators will be blinded to treatment assignment in the interim analysis. We will test our a priori hypotheses and suggest consideration of early stopping to the DSMB if either group shows an effect on the primary outcome using O'Brien-Fleming stopping bounds [45] (i.e., a significance level of 0.0054). We will retain a significance level of 0.049 for our primary hypothesis at project completion.

E2.2 Primary hypothesis

We hypothesize that compared to sham TMS+BCBT, Veterans receiving active TMS+BCBT will demonstrate superior improvements in suicidal ideation and fewer suicide attempts. Our primary outcome for this aim is a composite measure of suicide behavior based on occurrence of any of five types of suicidal behavior: death by suicide, suicide attempt, interrupted or aborted attempts, and suicide preparatory acts. This composite score is derived from the Columbia Suicide Severity Rating Scale (C-SSRS). The C-SSRS captures data on number of attempts, aborted attempts, and interrupted attempts. Number of suicide behaviors will be added across these categories to yield a total suicide events score. Death by suicide will be captured by review of medical records and death records. The main exposure variable of interest is the random treatment assignment. Our analytic approach will be an ANCOVA-type mixed effect regression model [72]. This means the outcome composite measure at follow-up time points (e.g., 3, 6, 12 months) will be regressed on baseline value of the outcome, design factors, and treatment assignment, dummy variables for time (baseline as reference) and interactions of treatment assignment and time dummies. Random intercepts and exchangeable error covariance structure will accommodate non-independence of observations owing to the repeated measures design.

The main effect of TMS as adjunctive to BCBT will be tested with the main effect of group assignment to the joint intervention condition. The time effect interactions of TMS assignment test hypotheses about the maintenance of gains at 3, 6 and 12 months. Our main hypothesis is that there is an immediate beneficial effect of TMS exposure. For our secondary outcome, (time to first suicide attempt over 12 months) we will use a Cox proportional hazards model analysis framework.

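### The primary outcome is described first as any-occurrence of five behaviours and then as a sum over categories that may be only three, with no distribution named; its stated detectable effect of .47 should be 0.49 by the plan's own formula

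*Combined protocol and SAP*

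**What the plan says.** E2.2 (Primary hypothesis) calls the primary outcome a "composite measure of suicide behavior based on occurrence of any of five types of suicidal behavior", listed as "death by suicide, suicide attempt, interrupted or aborted attempts, and suicide preparatory acts". It says that this composite score comes from the C-SSRS and continues: "The C-SSRS captures data on number of attempts, aborted attempts, and interrupted attempts". The next sentence is "Number of suicide behaviors will be added across these categories to yield a total suicide events score". For deaths it gives a source only: "Death by suicide will be captured by review of medical records and death records".

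On the model, E2.2 says: "Our analytic approach will be an ANCOVA-type mixed effect regression model", adjusted for baseline value and design factors, with random intercepts and follow-up at, for example, 3, 6 and 12 months. It names no distribution or link. E1.1 allows transformation to normality where needed and handles missing data by multiple imputation with sensitivity analyses. E2.3 refers to a generalized linear mixed model in the same manner as the primary analysis, again without a family, and chooses negative binomial regression for hospitalizations and crisis visits.

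E2.2.1 gives a detectable d of 0.50 unadjusted and .47 at a pre-post correlation of .2, with 65 per group. It acknowledges that its benchmark effects are for depressive symptoms. E2.1 says: "We will conduct 1 interim analysis and assess our primary aim when we have enrolled 32 persons per treatment group", at a level of 0.0054, with 0.049 kept for the end. Analyst and investigators are blinded to assignment at that look.

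**The concern.** Whether any event occurred and how many events occurred are different variables, and they need different models. The phrase about adding across categories directly follows a sentence naming three counts. If those three are meant, a participant with only preparatory acts scores zero and a suicide death does not enter the score. That contradicts the five-type definition a few lines above.

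The same variable is tested twice, at 0.0054 and at 0.049. If it is not fixed in advance, its components and its model could be settled after outcome data have been compared by arm. Readers also cannot tell what reduction in suicidal behaviour 130 participants could show: the power statement is in standard deviation units of a variable for which the plan gives no rate, mean or dispersion.

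**Working it through.** **The plan's own figure (E2.2.1).** Inputs: n = 65 per group, r = .2. The constant 16 corresponds to about 80% power at two-sided 5%; this is an assumption, as the section states neither for the primary outcome.

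- Unadjusted: sqrt(16/65) = 0.496. This reproduces the stated 0.50.
- Adjusted: sqrt(16 x (1 - 0.2²)/65) = sqrt(16 x 0.96/65) = 0.486, so 0.49. The stated .47 is not reproduced.
- To reach .47 at n = 65: r = sqrt(1 - 0.47² x 65/16) = 0.32.
- To reach .47 at r = .2: n = 16 x 0.96/0.47² = 69.5, about 70 per group.
- Power at d = .47, r = .2, n = 65 is 78.1%, about 2 points below 80%.

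**What d means on the event scale.** The plan gives no sham-arm risk for the composite, so 30%, 40% and 50% are assumptions. E2.2.1 assumes a 21% attempt risk over 12 months for the secondary outcome. Attempts are part of the composite, so 21% is a floor.

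For any-event, solve (p0 - p1)/sqrt([p0(1-p0) + p1(1-p1)]/2) = d, for d from 0.47 to 0.496:

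| Assumed sham risk p0 | Active-arm risk p1 | Relative reduction |
|---|---|---|
| 30% | 11.5%-10.6% | 62%-65% |
| 40% | 19.1%-18.1% | 52%-55% |
| 50% | 27.7%-26.6% | 45%-47% |

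For a count, assume a negative binomial with variance m + k·m², k = 1 or 3, and set the sham mean from P(any) = 1 - (1 + k·m0)^(-1/k). Solving (m0 - m1)/sqrt(mean of the two variances) = d over the same risks gives reductions of about 54% (50% risk, k = 1, d = 0.47) to 79% (30% risk, k = 3, d = 0.496).

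**Five categories versus three, any-event.** Exact enumeration of the pooled z-test, 65 per arm, two-sided 0.049, five-category sham risk 40%. The share of event participants with preparatory acts only is assumed to be 10%, 25% or 40%; deaths are ignored. Three-category sham risk is then 36%, 30% or 24%, all above the 21% floor.

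- Treatment halves risk on both lists: 71% power with five (40% v 20%); 64%, 54% and 43% with three.
- Treatment halves only the three-category risk, 25% share: 54% with three (30% v 15%); 45% with five (40% v 25%).

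All these event-scale figures use one result per person at a single time point, no dropout and no baseline covariate. They are not the power of the planned repeated-measures model.

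**The case against.** The best reply is that the plan describes one variable, a summed score. E2.2 speaks of a composite score with a baseline value, E2.2.1 uses a pre-post correlation and a mean difference, and the five-type sentence can be read as listing the components. This largely stands: a sum is the better-supported reading and yes/no the weaker one. It does not settle which components are summed.

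The plan also responds to skewness with its transformation clause. That clause leaves the choice until the data are seen, and it may suit a sparse count poorly. Interim blinding to assignment limits choosing the variable after the fact, but only partly, because coded arms must still be compared. The plan links its depression benchmarks to suicidality through pilot correlations above .55; those concern single suicide items on symptom scales, not behaviours.

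On deaths, the practical size is small. Applying the 0.8%-2.6% one-year mortality after an attempt, cited in the Background, to all 130 participants gives about 1 to 3 deaths (130 x 0.008 = 1.0; 130 x 0.026 = 3.4). No effect on the result has been shown. Nor does the plan say that visits after a death count as missing; it only fails to exempt them from imputation.

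A reader might infer that the three-count reading always costs power. The documents do not support that: the order reverses if treatment leaves preparatory acts unchanged, which the plan does not address.

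**Conclusion.** The point holds. As written, the primary variable is inconsistent: five behaviours by occurrence, then a sum whose components may be three. No family or link is chosen, although the plan chooses one for its other count. The printed .47 is wrong by the plan's own formula and should be 0.49. That error is small, and the undefined variable is the part that matters.

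The event-scale reductions, 45%-65% for any-event and about 54%-79% for an overdispersed count, rest on assumed sham risks of 30%-50% and, for the count, on assumed dispersions of 1 to 3. They show that a medium d can be a large reduction in events, so describing it as an effect of minimal clinical significance has no support for this outcome.

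A reader might go further and infer that the planned analysis is shown to be underpowered, or that preparatory acts and deaths are definitely excluded. Neither follows. The illustrations are not the planned model, and the wording allows all five categories to be summed.

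**What to change.** Before any look at outcome data by arm, including the interim:

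- State one primary variable consistent with the five listed behaviours. The summed count is closest to the text.
- Say that preparatory acts and deaths enter it, and that visits after a death are not imputed.
- Name a matching family and link, for example negative binomial for a count, and report any-event as a sensitivity analysis.
- Correct .47 to 0.49. Restate the detectable effect as a rate ratio or risk difference over stated assumed control rates, with dispersions for a count. E2.3.1 already uses a relative rate for hospitalizations.
- Remove or qualify the clinical-significance wording.

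The cost is rewriting the outcome and power paragraphs, with no new data collection. The downside is that the stated detectable effect will look less favourable and will rest openly on an assumed base rate. No gain in power or type I error is claimed; the benefit is one fixed variable and an effect that can be interpreted.

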Follow-up assessments will be conducted in-person or if necessary, by telephone 6, 12, and 24 months from the start of the intervention period. When assessments are conducted remotely, de-identified data may be collected by study staff at home due to remote connection issues (due to COVID-19). To reduce attrition, subjects will be paid \$50 in electronic funds transfer (EFT) or gift cards for completion of each follow-up appointment. Veterans participating in TMS+BCBT and neuroimaging will attend follow-up visits at 6, 12, and 24-months. Veterans only participating in TMS+BCBT will attend follow-up visits at 6- and 12-months. Veterans and matched controls participating only in the neuroimaging and cognitive battery will attend follow-ups at 6-, 12-, and 24-months.

D4.5.1 Blinded Assessment Administration: At the intervention endpoint visit, and 6-, 12-, and 24-month follow-up visits, assessments will be administered by study personnel who are blind to TMS condition (active vs. sham). For veterans who participate in the intervention component of the study, these assessments will not be administered by the study therapist or TMS provider even though they are also blind to the TMS condition. All study personnel will be blind to the study condition at baseline.

D5. Electronic Health Record (EHR) Data Extraction

Study staff will manually extract EHR data from participants' VA CPRS files. Extracted values will be entered into VA REDCap in anonymized format (by patients' study ID only). The initial data extraction will occur at baseline no later than one week of the participant's MRI Visit or beginning of intervention. Subsequent data extractions will take place six months, one year, and two years after starting intervention. At each time point (baseline,

+6months, +1 year, +2 years), data for the current month, and for each of the 12 prior months will be extracted.

D5.1 EHR predictor extraction:

Participants' CPRS files will be manually reviewed by the PI or by trained study staff. The following data types will be manually extracted from CPRS files: 1) Health services utilization; 2) pharmaceutical utilization; 3) changes in pharmaceutical utilization; 4) mental health diagnoses. Factors under consideration were selected based on prior demonstrations of machine learning applied to EHR ³⁹⁻⁴¹. Related information such as names of medications and medical conditions will also be extracted.

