be available in case of emergency. If a study participant reports significant deterioration but is not in immediate danger of hurting himself, we will take the following actions. First, we will inform patients about the procedures for contacting emergency services should they find themselves at risk for self-harm. Second, we will contact their outpatient psychiatrist or other primary clinician to inform them of their deterioration. Third, if there is an increase in suicidality during any TMS sessions, the TMS provider will immediately alert the designated study clinical

coverage personnel. In any event that a participant is acutely suicidal, the research staff member will walk the Veteran over to Interim Care or the ER for immediate safety assessment. All serious adverse events will be immediately recorded and reported to the Providence VAMC IRB and DSMB according to policy.

G2.8 Risks Related to Neuroimaging: There are no known physical, psychological, social, legal or other risks associated with participation in MRI at the level of magnetic field proposed here beyond those posed by the existence of an implanted non-MR safe metal device or metal fragment, or of claustrophobia. Multiple screens for contraindications are administered to eliminate significant risk. On rare occasions, subjects have reported heating of tattoos in the MRI. Participants with tattoos will be monitored for heating while in the MRI scanner.

The PI or trained study staff will discuss MRI visit procedures, including safety measures, in detail with the participant at the end of the baseline visit. Safety information is also included in the Informed Consent materials. They will be informed that there is a risk of claustrophobia during the scan; investigators and research technicians trained in screening procedures will evaluate for claustrophobia and take appropriate measures, including referrals to treatment. Subjects will be informed of the risk of heating from radiofrequency coils and instructed to inform the research technicians if this occurs. Subjects will also be informed that the scan session provided does not constitute a clinical scan and that researchers are not board- certified radiologists. If there is concern for a physical abnormality on structural scan, the PI will provide an appropriate referral. All serious treatment- emergent adverse events will be brought to the VA IRB as required in IRB protocols.

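### When the C-SSRS is missing, a suicide attempt documented in the chart or adverse-event file has no stated route into the primary composite or the time-to-first-attempt outcome

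*Combined protocol and SAP*

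**What the plan says.** E2.2 defines the primary outcome as a composite of death by suicide, attempts, interrupted or aborted attempts, and preparatory acts. On its source it says "This composite score is derived from the Columbia Suicide Severity Rating Scale (C-SSRS"). Records enter in one sentence: "Death by suicide will be captured by review of medical records and death records". The C-SSRS is given at baseline, endpoint and follow-up (Table 2). On mode, D4.5 says "Follow-up assessments will be conducted in-person or if necessary, by telephone".

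On the secondary outcome, E2.2 says "For our secondary outcome, (time to first suicide attempt over 12 months) we will use a Cox proportional hazards model analysis framework". It does not say where attempts or their dates come from, or when follow-up ends for a Veteran who misses a visit. On missing values, E1.1 says "missing data will be handled with multiple imputations (m=20) with assumptions checked with sensitivity analyses".

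Other sources are collected in parallel. Charts are extracted at baseline, and D5 adds: "Subsequent data extractions will take place six months, one year, and two years after starting intervention". Each extraction takes the current month and each of the 12 months before it. Table 5 includes emergency visits, inpatient mental-health stays and a suicidality item. Table 2 schedules a chart review of treatment use at baseline, endpoint and follow-up. G5 keeps adverse-event tracking files, and G2.7.3 says "All serious adverse events will be immediately recorded and reported to the Providence VAMC IRB and DSMB according to policy". No section connects any of these to the non-fatal components or to time to first attempt.

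**The concern.** Take a Veteran admitted after an attempt in month 8 who then has no 12-month C-SSRS, in person or by telephone. The 12-month extraction covers that month, and the attempt may also be in the adverse-event file. The admission could count toward the psychiatric hospitalization outcome in E2.3. Yet E2.2 offers no way for the attempt to enter the primary composite, whose 12-month value would be imputed. It also offers no rule for the Cox record.

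Two things are at stake. First, the attempt analysis rests on few events, so each lost one costs power. Second, a Veteran who has just made an attempt is plausibly likelier than others to miss the next interview. Missingness would then depend on the unobserved outcome. Imputation that assumes missing at random, or censoring that assumes independence, would understate events, and would bias the comparison if the share missed differed by arm. If the plan stays silent, the choice of sources falls to the analyst once data exist.

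**Working it through.** **1. The plan's own figure.** Inputs from E1 and E2.2.1: 65 per arm, 12-month attempt risk 21% and 4.5%, hazard ratio 0.19, alpha 0.05 (taken as two-sided), stated power 81.1%. The 21% is worded as a rate for the whole sample, but it works as the sham-arm rate.
- Implied hazard ratio: ln(0.955)/ln(0.79) = 0.195, close to 0.19.
- Expected attempts: 65 × 0.21 = 13.65 sham, 65 × 0.045 = 2.93 active, total 16.6.
- Two-proportion power: 81.3%.
- Freedman: Φ(√16.575 × (1 − 0.19)/(1 + 0.19) − 1.96) = Φ(0.81) = 79.1%.
- Simulated log-rank test (exponential times, full follow-up): about 84%.

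The stated 81.1% therefore reproduces, and it assumes that every attempt is observed. The plan gives no attrition rate.

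**2. Where a documented attempt goes when the C-SSRS is missing.**

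| Source | Collected | Stated role in composite | Stated role in time to attempt |
|---|---|---|---|
| C-SSRS | Endpoint, follow-up | All non-fatal acts | None stated |
| Medical and death records | Not scheduled in E2.2 | Death only | None stated |
| Chart extraction (D5) | 6, 12, 24 months | None | None |
| Adverse-event file (G2.7.3, G5) | Continuous | None | None |

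**3. Size of the loss, under assumed miss rates.** Simulation rules:
- A missed attempter is censored at the previous 3- or 6-month interview, or at baseline if there was none.
- Non-attempters miss the 12-month interview with probability 0.2 and are censored at 6 months (not in the 0% row).
- The test is log-rank at 0.05.

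| Attempters missed | Recovered from records | Expected events | Power |
|---|---|---|---|
| 0% | – | 16.6 | about 84% |
| 20% | none | 16.6 × 0.8 = 13.3 | about 76% (runs 75–77%) |
| 40% | none | 16.6 × 0.6 = 9.9 | about 63% (runs 62–64%) |
| 20% | half | 16.6 × 0.9 = 14.9 | about 81% |
| 40% | half | 16.6 × 0.8 = 13.3 | about 76% (runs 75–77%) |

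The last row must match the second, because half of 40% leaves 20% lost. As a cruder check, two-proportion power with 10%, 20% or 30% of attempts missed equally in both arms is 76.3%, 70.5% or 63.9%.

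**4. Sensitivity.**
- If every attempt in the first three months is known through treatment contact, power at 20% and 40% missed is about 78% and 70%.
- If 40% are missed in sham and 20% in active, power is about 52%. With the arms reversed it is about 83%. Differential loss moves the result in either direction.

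**The case against.** A reader might infer that the plan counts non-fatal acts only if the Veteran attends, discards known ones, and censors the Cox record at the last interview. The documents do not support that reading. No section excludes chart-documented acts, and no censoring rule is written, so censoring at the last interview is only the usual default. Telephone interviews are allowed. L.I.F.E. and SITBI also ask about suicidal behavior at endpoint and follow-up. A later C-SSRS might look back over a missed one, and E1.1 promises sensitivity analyses. At entry, the plan itself uses chart and C-SSRS together. These points limit the claim to a missing rule. They do not supply one: L.I.F.E. and SITBI have no stated role in either outcome, look-back is not described, and the sensitivity analyses are unspecified. Veterans in TMS+BCBT only have follow-ups at 6 and 12 months (D4.5), so nothing follows a missed 12-month interview.

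The records are also weaker than they look. Table 5 places suicidality among current and lifetime diagnoses, D5.2 averages values by quarter and year, and no dated attempt is listed. Nobody is assigned to search charts for adverse events after treatment ends. VA charts miss some non-VA care. All of this stands, so current extractions would need added fields and recovery would be partial.

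The sharpest objection is to a broad remedy. Because charts are extracted for everyone, imputing only where neither source covers the interval would score a silent chart as zero. Charts are a poor source for interrupted, aborted and preparatory acts, so missing values would become false zeros. That is right, and chart evidence should therefore be confined to actual attempts.

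**Conclusion.** The concern holds in a limited form. E2.2 leaves a documented attempt without a route into the primary composite or the time-to-attempt outcome when the C-SSRS is missing, although the trial already reviews the records where it would appear. In the plan's own scenario the cost to the attempt analysis is roughly 8 points of power if 20% of attempters are missed and 21 points if 40% are (84% to 76% and 63%). Recovering half of them restores about 5 and 13 points.

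These figures rest on assumed miss and recovery rates and on censoring at the previous interview, none of which the documents give. That attempters miss more interviews is plausible but not shown. Nothing here sizes the effect on the primary composite. The change is worth making because the event count is small and the rule can be fixed before the data are seen.

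**What to change.** In E2.2:

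- Count an actual suicide attempt, for both the composite and time to first attempt, if it is documented by C-SSRS or by chart or adverse-event record. Apply this to all 130 randomised Veterans over the same 12 months.
- Record the date and type of each documented attempt at the extractions already scheduled in D5. Have staff blind to arm review them; D5.1 assigns extraction to the PI or trained staff and does not mention blinding.
- State that Cox follow-up ends at the last date covered by interview or chart review.
- Keep interrupted, aborted and preparatory acts on the C-SSRS, with multiple imputation when the interview is missing. Do not read a silent chart as zero for them. Impute these components rather than the total, so that a documented attempt is kept.
- Report the interview-only result as a sensitivity analysis.

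The cost is SAP wording, two extraction fields, and time for blinded review. No visit or clinical procedure changes. One limit remains: an attempt treated outside the VA and never reported would be carried as event-free to the chart-review date. With half of the missed attempts recovered, simulation under that rule gives about 79% power at 20% missed and 75% at 40%, so most of the gain survives. The interview-only analysis shows how far the result depends on it.

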E2.2.1 Statistical power and sample size for our primary outcome: With 65 persons per group, Lehr's equation [73] instructs that minimum detectable standardized mean difference effect size difference (d) between treatment groups at the baseline assessment is $\text{sqrt}(16/n)$, where n is the per-group sample size, or 0.50 standard deviation units, a medium effect size in Cohen's effect size taxonomy [74]. Given the ANCOVA design, we will be able to detect a smaller effect depending upon the magnitude of the pre-post correlation (r) of the suicidal behavior composite outcome $\{d = \text{sqrt}([16(1-r^2)]/n)\}$, which under the assumption of a moderate correlation (r = .2) the minimum detectable effect size is $d = .47$. These are medium or typical effect size magnitudes [75] and are likely to describe effects of minimal clinical significance or practical importance. Of note, these are also comparable with prior TMS studies [64,65] who described effect sizes of .5-.52, and more recent studies indicating larger (d=.9) effect sizes of TMS used with medications [76]. While we recognize these are effect sizes for depressive symptoms, in our pilot work we found reduction in depressive and suicide-related symptoms to be highly correlated. For our secondary outcome, we used simulations to determine the minimum detectable difference. If we assume that 21% of the sample will experience a suicide attempt over 12 months follow-up, if the cumulative risk of suicide attempt is 4.5% over 12 months in the TMS+BCBT group (hazard ratio = 0.19) we

will have 81.1% power to detect such an effect using a type-I error rate of 5% in a Cox proportional hazards model framework.

E2.3 Secondary hypotheses

For this aim we hypothesize, compared to sham TMS+BCBT, Veterans who receive active TMS+BCBT will have superior improvements in psychosocial functioning and fewer psychiatric hospitalizations/crisis visits during the follow-up period. The outcomes for this aim are a)

WHODAS score b) number of psychiatric hospitalizations/crisis visits c) reduced suicide ideation as measured by the C-SSRS. The analysis for the psychosocial functioning outcome, (a), and the suicidal ideation severity score from the C-SSRS, (c), will be a repeated measures ANCOVA, as with the primary hypothesis, using a generalized linear mixed effect model. For part (b), the outcome will be a count variable, for which we will use negative binomial regression.

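### The primary test is the group main effect with baseline as the time reference, so it tests the arm difference at baseline and not the effect of TMS

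*Combined protocol and SAP*

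**What the plan says.** Four statements in section E2.2 (Primary hypothesis) define the primary test.

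- Outcome rows: "the outcome composite measure at follow-up time points (e.g., 3, 6, 12 months) will be regressed on baseline value of the outcome".
- Time coding: "dummy variables for time (baseline as reference) and interactions of treatment assignment and time dummies".
- Primary test: "The main effect of TMS as adjunctive to BCBT will be tested with the main effect of group assignment to the joint intervention condition".
- Role of the interactions: "The time effect interactions of TMS assignment test hypotheses about the maintenance of gains at 3, 6 and 12 months".

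The aim of the test follows directly: "Our main hypothesis is that there is an immediate beneficial effect of TMS exposure". Section E2.2.1 then gives the detectable "effect size difference (d) between treatment groups at the baseline assessment" as 0.50 SD with 65 per group.

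**The concern.** With reference-cell dummies and a full set of interactions, the coefficient for group is the arm difference at the reference visit and nothing else. E2.2 gives 3, 6 and 12 months an interaction each, which leaves baseline as the only possible reference, and baseline is what the text names. The coefficient chosen as the primary test is then a pre-treatment comparison, while the treatment effect sits in terms labelled as maintenance.

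The alternative is to take literally the restriction of the outcome to follow-up visits. Baseline is then not a level of time in the data, and the model as written cannot be fitted without dropping columns.

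At stake is the single primary p-value. Either it carries no information about TMS, or it refers to a visit picked by a software default. The interim look in E2.1 assesses the same primary aim, and E2.3 reuses this approach for the WHODAS and C-SSRS ideation outcomes, so the problem carries over to both.

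**Working it through.** **Inputs from the document.** 65 per arm (E1). Final significance level 0.049 (E2.1). Outcome rows, coding and primary coefficient as quoted from E2.2. Covariance, also from E2.2: "Random intercepts and exchangeable error covariance structure will accommodate non-independence of observations owing to the repeated measures design". Pre-post correlation 0.2 and detectable difference 0.50 (E2.2.1).

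**Assumptions.** Normal outcome with SD 1, complete follow-up, two-sided test at z = 1.96, exchangeable correlation r of 0.2 or 0.5 among all four visits, and a true effect of -0.5 SD at 3, 6 and 12 months with none at baseline. The normal outcome serves only to show what each coefficient estimates.

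**The plan's figure.** Lehr's formula gives √(16/65) = 0.496, which rounds to the stated 0.50. Power for d = 0.5 with 65 per arm is 81.3% at two-sided 0.05 and 81.1% at 0.049, so the choice of level hardly matters. (A separate matter: the adjusted figure of 0.47 does not reproduce at r = 0.2, because √(16 × 0.96/65) = 0.486.)

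**Step 1: what the coefficient means.** Write the mean as

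b0 + b1·G + b2·y0 + Σ g_k·T_k + Σ d_k·G·T_k, for k = 3, 6, 12 months,

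with G the arm and y0 the baseline value. At baseline every T_k is 0, so for a given y0 the arm difference is b1. At visit k it is b1 + d_k. The plan tests b1.

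**Step 2: follow-up rows only.** The columns are intercept, G, y0, three T_k and three G·T_k, which makes 9. In every remaining row T_3 + T_6 + T_12 = 1, which equals the intercept, and G·T_3 + G·T_6 + G·T_12 = G. Those two exact dependencies leave rank 9 - 2 = 7, confirmed numerically. Adding the balancing factors does not remove them. With baseline rows included, the rank is 9 of 9, so the software would report b1 without any warning. With follow-up rows only and 3 months as reference, there are 7 columns and the rank is 7.

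**Step 3: simulation, 2,000 trials per setting.** Each cell shows the mean estimate and the share of trials significant.

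| Model and term tested | r = 0.2 | r = 0.5 |
|---|---|---|
| Baseline rows in, baseline reference, no baseline covariate: group | -0.009; 4.9% | 0.000; 4.6% |
| As above with baseline covariate: group | -0.005; 0.5% | 0.000; 0.0% |
| As above with baseline covariate: 3-month interaction | -0.489; 60% | -0.500; 82% |
| Follow-up rows only, baseline covariate, 3-month reference: group | -0.496; 82% | -0.500; 91% |

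With no true effect, the last model rejects in 5.0% and 5.5% of trials.

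**Step 4: check by formula.** Adjusted for baseline, the standard error of the 3-month difference is √(2(1 - r²)/65). At r = 0.2 this is √(2 × 0.96/65) = 0.172, so 0.5/0.172 = 2.91 and power is Φ(2.91 - 1.96) = 83%. The interaction compares changes from baseline, with standard error √(2 × 2(1 - r)/65) = √(3.2/65) = 0.222. That gives 0.5/0.222 = 2.25 and power Φ(2.25 - 1.96) = 61%. Both agree with the table. Moving the test to the 3-month interaction, with the coding left alone, would therefore recover the effect but lose about 20 points of power at the plan's own correlation.

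**The case against.** The strongest reply is that the same sentence restricts the outcome to follow-up visits and describes an ANCOVA-type model, so baseline rows were never meant as outcomes and the group term cannot be a baseline contrast. E2.3 also calls the approach a repeated measures ANCOVA, where a group main effect often means the average over visits. That average is a sound test. With correlation 0.2 to baseline and 0.5 among follow-ups, simulations put its power at 92% to 94%. If software drops columns instead, the resulting group term is still a randomised comparison at some follow-up visit. The rejection rates near zero come partly from using baseline as both outcome and covariate. The phrase in E2.2.1 may be a slip and leaves the 0.50 unchanged.

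Much of this is fair. The sentence does contradict itself, and on the follow-up-only reading the fault is an unidentified visit and not an empty test. The near-zero rejection rates should be read together with the 4.6% to 4.9% obtained without the covariate, which is simply the type I error.

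None of it rescues the text. An average over visits is not what the stated dummy coding produces, and it is not an immediate effect. If baseline were one of the visits averaged, an effect of 0.5 would shrink to 0.5 × 3/4 = 0.375. That the intent can be guessed does not settle which contrast is primary, and the 3-month difference and the follow-up average are different quantities with different power.

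**Conclusion.** The concern holds, and the plan must be corrected before the analysis. No literal reading of E2.2 makes the named coefficient the effect the trial is meant to test. With baseline rows its expected value is zero whatever TMS does. Without them it is not identified alongside the three interactions.

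This conclusion is algebraic and does not depend on the outcome distribution, the correlations or the effect size. The power figures do depend on them. They assume a normal outcome and complete follow-up, whereas the endpoint is a composite built from event counts, so they illustrate the contrast between codings and are not power estimates for this trial.

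**What to change.** In E2.2:

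- State that the outcome rows are the 3-, 6- and 12-month visits only, as a fixed list and not as examples, with the baseline value as a covariate.
- Make 3 months the reference for time and name the group coefficient, now the 3-month difference, as the single primary test. This matches the stated immediate effect and the endpoint visit, which D4.5 places at 12 weeks.
- Reword the sentence on interactions. Two remain, comparing the effect at 6 and at 12 months with that at 3 months, and these test maintenance.

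In E2.2.1, replace the mention of the baseline assessment with the 3-month assessment.

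A prespecified average over the three follow-up visits would also be a valid test, but it would need the hypothesis reworded, since it is not an immediate effect.

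The cost is a few words in adjoining sentences of E2.2 and one phrase in E2.2.1. The interim test in E2.1 and the two mixed-model outcomes in E2.3 should follow the corrected model. No new data, visits or participants are needed.
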